## Background

Osgood-Schlatter is a growth-related condition involving multiple types of tissue in the tendon-bone interface at the tibial tubercle. Osgood-Schlatter affects one in ten adolescents causing persistent pain, reduced peak torque during knee extension, and reduced ability to maintain participation in sports and physical activity. Rate of torque development is linked to athletic performances, and reductions in rate of torque development is associated with decreased neuromuscular functioning and pain chronicity. As peak torque is reduced in Osgood-Schlatter, changes in rate of torque development is likely also affected, but this has not yet been investigated. This insight could help characterize the condition and guide management.

## Aim

To investigate if early and peak rate of torque development during knee extension is reduced in the asymptomatic limbs or during knee flexion in adolescents with Osgood-Schlatter, compared to a matched group of asymptomatic adolescents.

## Study design

A cross-sectional case control study.

## Methods

The study design and analysis strategy have been published along with a trial registration (ClinicalTrials.gov NCT05789095). The study will include 13 adolescent participants with Osgood-Schlatter and a group of 13 pain free controls matched on sex, age, and sports participation on the group level. Testing will include bilateral rate of torque development measurements of knee extension and flexion, with a fixated handheld dynamometer, during a single test-session lasting approximately two hours. The examiner responsible for strength-testing will be blinded to case-status. Along with anthropometric data, participants will perform the anterior knee pain provocation test to assess pain-response to sustained knee loading, a countermovement jump test to assess power and jump height, and provide patient-reported measures of condition severity, pain, disability, and quality of life. Data collection will start February 2023 and is expected to be completed by May 2023.

## Expected results and implications

As the condition affects the knee-extensor mechanism, we expect lower levels of rate of torque development in the affected knee during extension. The main interest, however, is if the level of rate of torque development is also significantly reduced in non-symptomatic limbs or in knee flexion, in cases compared to symptom-free healthy controls. This would indicate inhibited neuromuscular function on a central level, due to other factors than local tissue pathology, such as pain chronicity, central muscle inhibition, or other drivers.

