## Rationale and background

Osgood-Schlatter is an apophysitis of the tibial tubercle occurring in its primary form during adolescence. The condition affects one out of ten, and is even more prevalent in highly active adolescents.

Adolescents with Osgood-Schlatter experience a reduced ability to participate in sports and physical activities. A previous study from our group found that maximal strength and pain during isometric knee extension strength test on adolescents with Osgood-Schlatter, was moderately correlated to self-reported outcomes in terms of knee-related quality of life, sports participation satisfaction, mental health and pain beliefs. Rate of force development is a measure of explosive strength, or the ability to develop force over a short time period and is correlated to explosive actions, such as sprinting and jumping. In patients with prolonged or acute knee pain, rate of force has been found to be decreased. Several studies have shown that changes in rate of force development is linked to decreased neuromuscular function, and thereby is affecting sports function and activities of daily living. No previous investigations of rate of force development have been published for this group.

Measuring rate of force development in adolescents with Osgood-Schlatter, might further explain the relationship between features of knee function and self-reported outcomes. To account for differences in stature and bodyweight, normalizing for these variables will provide the more precise measure of rate of torque, often used in biomechanical research.

It would be interesting to investigate if rate of torque development is affected in this group. If it is, it could be explained by the theory that pain in local tissue, is affecting the ability to activate maximal muscle contraction in a limited time span. Furthermore, we suspect that the non-affected leg in the Osgood-Schlatter group, also will have a lower rate of torque development. This is based on the hypothesis that Osgood-Schlatter, affects the central nervous system due its chronicity, and therefore the ability to develop maximum rate of torque.

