## Hypotheses

The hypotheses being tested are

1. that adolescents with Osgood-Schlatter, has a lower knee extension RTD in their affected knee compared to matched controls
2. that adolescents with Osgood-Schlatter, has a lower knee extension RTD in their affected knee compared to their potential asymptomatic knee
3. that adolescents with Osgood-Schlatter, has a lower knee extension RTD in their potential asymptomatic knee compared to matched controls
4. that adolescents with Osgood-Schlatter, has a lower knee flexion RTD in their affected knee compared to matched control
5. that adolescents with Osgood-Schlatter, has a lower knee flexion RTD in their affected knee compared to their potential asymptomatic knee
6. that adolescents with Osgood-Schlatter, has a lower knee flexion RTD in their potential asymptomatic knee compared to matched controls
7. That levels of either early or late rate of torque development is negatively correlated with pain during rate of torque development-testing, countermovement jump height or power, anterior knee pain provocation test score, current pain, pain duration, KOOS child 'Pain', 'Sport/rec' or 'QoL' subscales,

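### Reduced knee-flexion RTD in the painful limb alone would satisfy the plan's criterion for a central effect, because the flexion branch names no limb

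*Combined protocol and SAP*

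**What the plan says.** **Aim.** The study asks whether early and peak RTD "is reduced in the asymptomatic limbs or during knee flexion in adolescents with Osgood-Schlatter". Asymptomatic limbs and knee flexion are joined by an "or", and no limb is given for flexion.

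**Expected results and implications.** A lower extension RTD in the affected knee is expected, because the condition affects the extensor mechanism. The main interest is whether RTD is "also significantly reduced in non-symptomatic limbs or in knee flexion, in cases compared to symptom-free healthy controls". The inference follows at once: "This would indicate inhibited neuromuscular function on a central level, due to other factors than local tissue pathology". Pain chronicity, central muscle inhibition and other drivers are offered as examples.

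**Rationale and background.** Two mechanisms are given. The first is local: "pain in local tissue, is affecting the ability to activate maximal muscle contraction in a limited time span". The second is central and is attached to the other limb: "we suspect that the non-affected leg in the Osgood-Schlatter group, also will have a lower rate of torque development", followed by "This is based on the hypothesis that Osgood-Schlatter, affects the central nervous system due its chronicity". Flexion is not mentioned in this section.

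**Hypotheses.** Flexion has three separate contrasts. In hypothesis 4 the Osgood-Schlatter group "has a lower knee flexion RTD in their affected knee compared to matched control". In hypothesis 5 it "has a lower knee flexion RTD in their affected knee compared to their potential asymptomatic knee". Hypothesis 6 compares flexion of the asymptomatic knee with controls. Hypothesis 3 is the corresponding between-group contrast for extension of the asymptomatic knee.

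**Statistical methods.** Only an unpaired two-sided t-test (or the Wilcoxon rank sum test) is specified. There is no correction for multiple testing.

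**The concern.** Hypothesis 4 is measured in the painful limb, but a significant result there fits the wording under Expected results. The central interpretation could then be reached when neither contrast in an asymptomatic limb (hypotheses 3 and 6) shows a reduction, and even when hypothesis 5 indicates that the deficit is on one side. The Rationale's local mechanism, pain limiting fast maximal contraction, is not restricted to the extensors and could produce the same result. Nothing in the plan says how the pattern of hypothesis 4 positive with hypotheses 3 and 6 not positive is to be read.

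At stake is the inference the plan itself calls its main interest: whether a reduction reflects something beyond the local tissue. The tests themselves are not in question. The gap lies in what may be concluded from them.

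**Working it through.** **1. Which tests meet the criterion.**

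| Hypothesis | Contrast | Meets Expected results wording | Comes from an asymptomatic limb |
|---|---|---|---|
| 1 | Extension, affected knee vs controls | No (expected effect of the condition) | No |
| 3 | Extension, asymptomatic knee vs controls | Yes | Yes |
| 4 | Flexion, affected knee vs controls | Yes | No |
| 6 | Flexion, asymptomatic knee vs controls | Yes | Yes |

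Hypotheses 2 and 5 compare sides within cases, so they are not comparisons with controls. Hypothesis 4 is the only row where the criterion is met without evidence from an asymptomatic limb.

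**2. The plan's own figure.** Inputs from Sample size: means 6 vs 3 Nm/kg/s, SD 2.6, two-sided 5%, 80% power. The standardised difference is d = 3/2.6 = 1.154. The two-sample t-test (noncentral t) gives n = 12.83 per group, rounded up to 13, with power 80.6% at 13 per group. The stated 13 is reproduced.

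**3. How often the criterion would be met if the flexion deficit were confined to the affected limb.**

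Assumptions not in the documents:
- the flexion effect: 50% lower (6 × 0.50 = 3) or 30% lower (6 × 0.30 = 1.8) in the affected limb, and zero in the asymptomatic limb;
- correlation between a participant's test results: 0.5 to 0.8;
- cases with an asymptomatic knee: 8 or 13 of 13.

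Method: 20,000 simulated trials per setting, control mean 6, SD 2.6, 13 per group, one RTD variable. Unpaired t-tests were used for hypotheses 3, 4 and 6 and a paired t-test for hypothesis 5. Each counts only if significant at two-sided 5% in the lower direction.

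| Event | 50% deficit | 30% deficit |
|---|---|---|
| Hypothesis 3, 4 or 6 positive (criterion as written) | about 80% | about 40% |
| Hypothesis 3 or 6 positive (asymptomatic limb required) | 4-5% | 4-5% |
| Hypothesis 4 the only support | 76-77% | about 36% |

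The first row is essentially the power of hypothesis 4, and for the 50% deficit it matches the 80.6% in step 2. The second row is the false-positive rate of two tests counted in one direction. Under independence it is 1 − (1 − 0.025)² = 4.9%, and correlation lowers it a little. With the 50% deficit, hypotheses 4 and 5 are both positive while 3 and 6 are not in 63-77% of trials, so the plan's own side-to-side contrast would often point to one limb.

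**4. Can a non-significant hypothesis 6 be read as a deficit on one side only?** The simulation was repeated with an equal flexion deficit in both limbs. Among trials where hypothesis 4 is significant, hypothesis 6 is non-significant in 9-26% (50% deficit) or 26-54% (30% deficit). A rule of that kind would often mislabel a bilateral deficit.

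**The case against.** **The sections do not contradict each other.** A reader might infer that the plan gives two competing definitions of a central effect. It does not. The Rationale states an expectation about the non-affected leg. It sets no criterion and excludes nothing, and the Aim and Expected results agree with each other. This objection stands.

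**Flexion has an implied purpose.** Expected results begins from the extensor mechanism, so flexion can be seen as testing muscles outside it, just as the other leg is a limb outside it. That is a legitimate design idea. But the plan never argues that flexion of a painful knee is free of local pain inhibition, and the Rationale's local mechanism is not limited to extension. The phrase about other drivers does not help, because those drivers still fall under factors other than local pathology.

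**It is a summary paragraph, not a decision rule.** This is true. Estimates, effect sizes, exact p-values and confidence intervals are to be reported for separately listed hypotheses, so the pattern would be visible to a reader. The stated interpretation would still be unsupported by it.

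**The 80% is the design's own power.** It largely is. It follows from assuming a limb-confined flexion deficit of the size used for planning, and says nothing about how likely such a deficit is.

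**Pain is recorded at each attempt.** It is, but hypothesis 7 only correlates pain with RTD. It is not linked to the local-versus-central question.

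**Conclusion.** The point holds as a gap in interpretation. The Aim and Expected results name no limb for flexion, and Expected results treats reduced flexion RTD as sufficient for a central effect that excludes local pathology. Hypothesis 4 alone would therefore meet the criterion. The criterion is broader than the Rationale rather than inconsistent with it.

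Its size is conditional. If the flexion deficit were confined to the affected limb, the criterion would be met in about 80% of trials (50% deficit) or 40% (30% deficit), against 4-5% if hypothesis 3 or 6 were required. The effect sizes, the correlations and the number of asymptomatic knees are assumptions; the documents give no flexion effect size. A reader might take the 80% as the chance that this study reaches a wrong central conclusion. The documents do not support that, because they do not say how probable a limb-confined flexion deficit is.

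Nor does a significant hypothesis 4 with a non-significant hypothesis 6 establish that the deficit is limb-specific. At this sample size that pattern also arises often when both limbs are equally affected. The wording should be changed before results are interpreted; the hypotheses and measurements can stay as they are.

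**What to change.** 1. Reword the Aim and Expected results so that a central interpretation requires lower RTD than controls in the asymptomatic limb (hypothesis 3 or 6).
2. Keep hypothesis 4 as a test. State that, alone, it will be reported as a flexor deficit in the affected limb that does not separate central from local causes.
3. State that hypothesis 4 will be read with the estimates and 95% confidence intervals of hypotheses 5 and 6. Call the deficit limb-specific only if the within-case side difference in hypothesis 5 supports it; otherwise call it inconclusive. Do not infer it from a non-significant hypothesis 6.
4. Add a paired analysis for hypothesis 5 to Statistical methods, which now specifies only unpaired comparisons.

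**Cost.** A few sentences and one added analysis, with no new measurements. The real downside is that the central claim would rest on cases who have an asymptomatic knee, whose number the plan does not fix, so the claim becomes harder to make.

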### Participants

#### Inclusion criteria

- Patients must be 9-16 years of age
- Presence of pain for 12 weeks or more
- Pain at tibial tubercle during loading activities
- Palpable pain at the tibial tubercle

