#### Clinical examination and treatment

The study procedures will be conducted by two examiners (JL and HS). JL will be aware of the case status and conducts the screening and preliminary testing. To avoid bias, examiner HS will be blinded for the case status during trial and will not know the Numerical pain Rating Scale-scores (NRS, 0-10, 'no pain' to 'worst pain imaginable') of the participants during testing. To strengthen the inter-reliability, the examiners will not change roles during the study.

The session starts with JL examining the potential participant in the OSD-case group, for Osgood-Schlatter. If the Osgood-Schlatter diagnosis is made, the participant is then enrolled. For the potential participant in the control group, JL screens for potential injury or pain in relation to the knee joint. In the absence of relevant pathology, the control-participant is enrolled.

Then, JL measures length of the lever arm and variables for peak hight velocity assessment. Participants will then answer the patient-reported outcome measures together with their parent/guardian.

For the rate of force development tests, HS will enter the room and conduct the tests as described below. For each attempt the participant will write down their NRS-rating on a piece of paper, out of sight from HS.

Before the rate of force development test is conducted, the participants are told that they can always abort the test, if they perceive that pain rises to such a degree that they can't continue the

testing, or they start feeling fearful or uncertain of their symptoms. They are ultimately told that potential pain felt during testing are not harmful and will subside within 24 hours, as is our experience from multiple earlier conducted tests.

HS leaves the room, for JL to conduct the Anterior Knee Pain Provocation test and save the NRS results.

HS returns to conduct the Counter Movement Jump Test, again blinded for the participants NRS-scores, which are written down on a piece of paper. HS leaves the room, and JL either treats the patient (case-group) or hands out compensation for participating (control-group).

Cases and controls will be instructed not to take any pain medication 24 hours prior to any assessment to ensure that this does not affect measurements.

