### Knee flexion

The participant is lying prone, with hip in neutral position,  $0^\circ$ . The knee is flexed about  $20^\circ$ , with the leg resting on the testers fist wedged between the examination table and the ankle. The participant will be instructed to hold onto the side of the examination table. A strap fixated to the floor, is used to fixate the handheld dynamometer. The dynamometer is placed central to the line of lever demarcation, approximately 2cm proximal to the lateral malleolus.

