### Outcome measures

The outcome measures are rate of torque development and NRS-values in relation to the force-measurements. To calculate the rate of torque (Nm/s/kg), the rate of force development-variables (N/s) is multiplied with length of the lever (m) and divided with the participant's bodyweight (kg).

Outcome variables related to the specified hypotheses are rate of torque development during 0-100 ms, 0-200 ms, peak RTD, and time to peak force during knee extension and knee flexion for both cases and controls.

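### Low RTD in flexion or in the other knee is to be read as not due to local tissue pathology, but no planned analysis checks that those tests were free of pain

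*Combined protocol and SAP*

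**What the plan says.** Under Expected results and implications, lower RTD in the affected knee during extension is expected. The main interest is whether RTD "is also significantly reduced in non-symptomatic limbs or in knee flexion, in cases compared to symptom-free healthy controls". The interpretation is fixed in advance: "This would indicate inhibited neuromuscular function on a central level, due to other factors than local tissue pathology".

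Three case-control hypotheses carry that interpretation: 3 (extension, other knee), 4 (flexion, affected knee) and 6 (flexion, other knee). Hypothesis 4 is that the case group "has a lower knee flexion RTD in their affected knee compared to matched control". The other knee is described only as potentially asymptomatic.

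Pain during testing is measured: "For each attempt the participant will write down their NRS-rating on a piece of paper". Under Outcome measures it has formal status: "The outcome measures are rate of torque development and NRS-values in relation to the force-measurements". Hypothesis 7 expects RTD to correlate negatively with pain during RTD testing.

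Statistical methods lists RTD and time-to-peak variables for an unpaired t-test or Wilcoxon rank sum test. Pain scores are not in that list, and no method is given for hypothesis 7.

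**The concern.** A deficit in a limb or movement away from the injured extensor mechanism is evidence for a central cause only if local pain was absent while that limb or movement was tested. The plan's own rationale makes local pain a live competing explanation: it offers the theory that "pain in local tissue, is affecting the ability to activate maximal muscle contraction" in a short time span. Entry requires "Palpable pain at the tibial tubercle" and pain there on loading, and hypothesis 4 then asks for a maximal flexion effort from that same knee.

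If some of these tests hurt, a reduction caused wholly or partly by pain at that moment would be reported as arising from something other than local pathology. The scores that could inform the question are already collected, but nothing in the analysis or in the wording of the conclusion depends on them.

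**Working it through.** **1. The plan's own figure.** Inputs from Sample size: 6 vs 3 Nm/kg/s, SD 2.6, two-sided 5%, 80% power. d = 3/2.6 = 1.154. The exact two-sample t calculation gives n = 12.83, so 13 per group, with power 80.6% at 13. The stated 13 reproduces, and no sample-size figure is in dispute.

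**2. What stands between each contrast and the central reading.**

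| Hypothesis | Test in cases | What the plan does to establish that the test was painless |
|---|---|---|
| 3 | Extension, other knee | No pain-free criterion for that knee; no use of pain scores by leg |
| 4 | Flexion, affected knee | Knee is painful by entry criteria; no use of pain scores by movement |
| 6 | Flexion, other knee | As for 3 |

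Under Risks and adverse events, pain leads to exclusion only when testing cannot continue. Painful but completed attempts stay in all three comparisons.

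**3. Can hypothesis 7 serve as the check?** It does not say which limb or movement is meant, and it asks whether pain and RTD are associated, not whether pain was absent. It is also insensitive. By the Fisher z approximation, the correlation detectable with 80% power is tanh((1.960 + 0.842)/√(n − 3)):

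- 13 cases: tanh(2.802/√10) = tanh(0.886) = 0.71.
- All 26 participants: tanh(2.802/√23) = tanh(0.584) = 0.53. This version mixes pain with case status.

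A null correlation would therefore not show that pain played no part.

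**4. Could pain alone produce the result? (Illustration only.)** The documents give no frequency of pain in flexion or in the other knee, and no effect of pain on RTD in this setting. Suppose that pain halves RTD (6 to 3) in a share f of cases and that there is no central effect. The mean difference is 3f. With SD 2.6 and 13 per group, the chance of a significant result is:

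| Share f | Difference | Chance of p < 0.05 |
|---|---|---|
| 25% | 0.75 | 11% |
| 50% | 1.50 | 29% |
| 75% | 2.25 | 56% |
| 100% | 3.00 | 81% |

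Holding the SD at 2.6 is slightly generous. A mixture widens the case SD to √(2.6² + 9f(1 − f)), which is √(6.76 + 2.25) = 3.0 at f = 50%, so the middle rows would be somewhat lower.

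A milder assumption gives much less. Take a within-case correlation of −0.3 to −0.5, a pain-score SD of 2, and 25–50% of cases scoring 3. The shift is r × (2.6/2) × 3 × f, that is 0.29 to 0.98 Nm/kg/s, significant in about 6–15% of studies. Those inputs are not fully consistent: scores of 3 in 25–50% of cases and 0 in the rest imply an SD of 3√(f(1 − f)) = 1.3 to 1.5. With that SD the shift is 0.45 to 1.30, significant in 7–23%. The range is wide because its driving inputs are all assumed.

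**5. What a painless-attempt analysis can deliver.** Assumed numbers of painless cases against all 13 controls, at 6 vs 3 and SD 2.6. Half-width = t(0.975, 11 + n) × 2.6 × √(1/13 + 1/n).

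| Cases n | Power | 95% CI half-width (Nm/kg/s) |
|---|---|---|
| 13 | 81% | 2.1 |
| 10 | 74% | 2.3 |
| 8 | 68% | 2.4 |
| 6 | 60% | 2.7 |
| 4 | 47% | 3.2 |

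This is usable as an estimate with its interval, but not as a significance gate. Controls removed under the same rule would lower these figures further.

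**The case against.** The best defence is that test pain is not ignored. It is rated at each attempt, named as an outcome and related to RTD in hypothesis 7. A reader might infer that the scores go unused, and that would be wrong. What stands is narrower: none of these uses establishes that flexion or other-knee tests were painless.

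Three further inferences are tempting and unsupported.

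- **Pressure on the tubercle.** For flexion, "The participant is lying prone, with hip in neutral position", which might suggest that the table presses on a tender tubercle. The same section has the leg resting on the tester's fist between table and ankle. Nothing says the tubercle bears on the table, so there is no basis here for asking that the position be changed.
- **Bilateral cases.** The provocation-test section allows for a most affected knee, and bilateral cases are not excluded. But a potential asymptomatic knee may simply mean one that the case happens to have, in which case bilateral cases contribute no limb to hypotheses 2, 3, 5 and 6. What is missing is an operational definition.
- **A reversed conclusion.** A reader might say the study would report the opposite of the truth. The sentence is an expectation, not a decision rule, and it leaves the non-local cause open. It still excludes local pathology, which is the unsupported step.

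There are also fair limits on any remedy. The pain score records no site, so a non-zero score may be exertional discomfort. Temporary pain and soreness are expected in both groups, so a restriction applied to cases alone would be lopsided. Painless cases may be milder, so losing the effect among them would not prove that pain caused it.

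**Conclusion.** The point holds as a gap between result and interpretation. As planned, a reduction under hypothesis 3, 4 or 6 would be attributed to something other than local tissue pathology with no check that local pain was absent in that leg and movement. Hypothesis 4 is the most exposed, because it uses the painful knee.

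The documents do not allow the bias to be sized. The chance that pain alone yields a significant difference runs from about 6% to 81% in the illustrations above, depending entirely on assumed pain frequency and effect. The case for change rests on the missing check, not on any one of those figures. The RTD comparisons remain valid as descriptions of group differences; it is the causal reading that needs the added condition.

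**What to change.** Amend Statistical methods and Expected results and implications as follows.

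1. Report pain scores during RTD testing by group, leg and movement.
2. Include a case's other knee in hypotheses 2, 3, 5 and 6 only if it has no tubercle tenderness at screening and no current pain on loading. State how many cases contribute.
3. Pre-specify a sensitivity analysis of hypotheses 3, 4 and 6 restricted to painless attempts, with the same pain-score rule for cases and controls and a stated way of summarising the remaining attempts. Report the difference with its 95% interval, not as a pass/fail gate.
4. Make the conclusion conditional. If pain was present in that leg and movement and the sensitivity estimate does not support a similar reduction, report *reduced; local pain not excluded*.

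Cost: analysis and wording. The pain scores are already collected; at most, screening must record tenderness and loading pain for both knees. Requiring a pain-free other knee may leave fewer than 13 cases for hypotheses 2, 3, 5 and 6. The painless subset will be smaller and possibly milder, and the score has no site, so the analysis can support or weaken the central reading but cannot settle it.
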